2.0 STUDY SUMMARY

Study Title:	Prospective, multi-center, single-arm study of the Shockwave Medical M ⁵⁺ Peripheral Intravascular Lithotripsy (IVL) System in calcified peripheral arteries (Disrupt PAD+)
Study Objective:	The objective of this study is to assess the safety and performance of the Shockwave M ⁵⁺ Peripheral IVL System to treat calcified peripheral arteries in pre-market countries, and to assess continued safety and effectiveness in the US.
Study Device(s):	Shockwave Medical M ⁵⁺ Peripheral IVL System
Indications for Use:	The Shockwave Medical M ⁵⁺ Peripheral IVL System is indicated for lithotripsy-enhanced, low-pressure balloon dilatation of lesions, including calcified lesions, in the peripheral vasculature, including the iliac, femoral, ilio-femoral, popliteal, infra-popliteal, and renal arteries. This device is not intended for use in coronary, carotid, or cerebrovascular arteries.
Study Design:	Prospective, multi-center, single-arm study of the M ⁵⁺ Peripheral IVL system to treat calcified peripheral arteries.
Enrollment:	A minimum of 40 lesions in up to 40 subjects at up to 10 sites in Australia, New Zealand and the US will be enrolled with the aim of treating at least 20 target lesions with the 8.0 mm IVL catheter. A maximum of three target lesions may be treated per subject.
Subject Population:	Subjects with moderate and severely calcified iliac and femoropopliteal artery disease presenting with Rutherford Category 2 to 5.
Study Duration / Follow-Up Period:	Approximately 6 months of enrollment at up to 10 sites in Australia, New Zealand and the US. Study subjects will be followed through discharge, 30 days, 6 and 12 months. Duplex Ultrasound (DUS) assessments will be completed at 12 months. Total anticipated study duration is 18 months.
Primary Safety Endpoint	Major Adverse Events (MAE) at 30 days defined as: 
 • Need for emergency surgical revascularization of target limb • Unplanned target limb major amputation (above the ankle)

	No.: CP 64007	REV. D
	TITLE: Disrupt PAD+ Study	
	CLASS: CLINICAL PROTOCOL	PAGE 7 OF 57

	
 • Symptomatic thrombus or distal emboli that require surgical, mechanical or pharmacologic means to improve flow and extend hospitalization • Perforations that require an intervention, including bail-out stenting
Primary Performance Endpoint:	
 • Technical success defined as final residual stenosis $\leq 30\%$ without flow-limiting dissection (\geq Grade D) of the lesion by angiographic core lab
Secondary Endpoints:	
 • IVL Technical success defined as residual stenosis $\leq 30\%$ without flow-limiting dissection (\geq Grade D) of the lesion post-IVL by angiographic core lab • Procedural success defined as final residual stenosis $\leq 30\%$ without any flow-limiting dissection (\geq Grade D) in all target lesions by angiographic core lab • Major Adverse Events (MAE) at 6 and 12 months • Primary patency at 12 months defined as freedom from clinically-driven target lesion revascularization (TLR) and freedom from restenosis determined by duplex ultrasound or angiogram $\geq 50\%$ stenosis • Clinically-driven target lesion revascularization (TLR) at 30 days, 6 and 12 months • Ankle-brachial index (ABI) at 12 months, reported as change from baseline • Rutherford Category at 30 days, 6 and 12 months, reported as change from baseline
Study Inclusion Criteria:	
General Inclusion Criteria
 
 1. Subject is able and willing to comply with all assessments in the study. 2. Subject or subject's legal representative have been informed of the nature of the study, agrees to participate and has signed the approved consent form. 3. Age of subject is > 18. 4. Rutherford Clinical Category 2, 3, 4 or 5 of the target limb(s). 5. Estimated life expectancy > 1 year.

	No.: CP 64007	REV. D
	TITLE: Disrupt PAD+ Study	
	CLASS: CLINICAL PROTOCOL	PAGE 8 OF 57

	
6. Subject is intended to undergo treatment with Shockwave M⁵⁺ Peripheral IVL System for de novo lesions of the ilio-femoropopliteal arteries.
 
Angiographic Inclusion Criteria
 
7. Single or multiple de novo target lesion(s) located from the common iliac to the femoropopliteal artery, in one or both limbs.
 
8. Target lesion reference vessel diameter is between 3.5mm and 10.0mm by visual estimate.
 
9. Target lesion is $\geq 70\%$ stenosis by investigator via visual estimate.
 
10. Target lesion length is ≤ 200mm for lesions 70-99% stenosed. Target lesion can be all or part of the 200mm treated zone.
 
11. Chronic total occlusion, lesion length is ≤ 100mm of the total ≤ 200 mm target lesion.
 
12. Subject has at least one patent tibial vessel on the target leg with runoff to the foot, defined as no stenosis $> 50\%$.
 
13. Calcification is at least moderate defined as presence of fluoroscopic evidence of calcification: 1) on parallel sides of the vessel and 2) extending $> 50\%$ the length of the lesion if lesion is ≥ 50mm in length; or extending for minimum of 20mm if lesion is < 50mm in length.

Study Exclusion Criteria:
	
General Exclusion Criteria
 
 1. Rutherford Clinical Category 0, 1, and 6. 2. Subject has active infection requiring antibiotic therapy. 3. History of endovascular or surgical procedure on the target limb within the last 30 days or planned within 30 days of the index procedure. Note: Concomitant IVL treatment to facilitate large bore access at the time of procedure is allowed. 4. Subject in whom antiplatelet or anticoagulant therapy is contraindicated. 5. Subject has known allergy to contrast agents or medications used to perform endovascular intervention that cannot be adequately pre-treated. 6. Subject has known allergy to urethane, nylon, or silicone. 7. Myocardial infarction within 60 days prior to enrollment. 8. History of stroke within 60 days prior to enrollment.

	No.: CP 64007	REV. D
	TITLE: Disrupt PAD+ Study	
	CLASS: CLINICAL PROTOCOL	PAGE 9 OF 57

	
9. Subject has acute or chronic renal disease defined as serum creatinine of >2.5 mg/dL or >220 umol/L, unless on dialysis.
 
10. Subject is pregnant or nursing.
 
11. Subject is participating in another research study involving an investigational agent (pharmaceutical, biologic, or medical device) that has not reached the primary endpoint.
 
12. Subject has other medical, social or psychological problems that, in the opinion of the investigator, preclude them from receiving this treatment, and the procedures and evaluations pre- and post-treatment.
 
13. The planned use of specialty balloons, re-entry or atherectomy devices in the target lesion(s).
 
Angiographic Exclusion Criteria
 
14. In-stent restenosis within 10mm of the target zone.
 
15. Target lesions distal to the popliteal artery.
 
16. Evidence of aneurysm or thrombus in target vessel.
 
17. No calcium or mild calcium in the target lesion.
 
18. Target lesion within native or synthetic vessel grafts.
 
19. Subject has more than three target lesions requiring treatment.
 
20. Subject has significant non-target lesion (>50% stenosis or occlusion) within the target limb (e.g. iliac, common femoral or below-the-knee) not successfully treated prior to treatment of the target lesions.
 
21. Failure to successfully cross the guidewire across the target lesion; successful crossing defined as tip of the guidewire distal to the target lesion in the absence of flow limiting dissections or perforations.

Study Statistical Methods:	Descriptive statistics will be reported.
Study Sponsor/Study Management Contact:	
Shockwave Medical, Inc. [name] [name] USA
 
Contact: [name] Title: Senior Director, Clinical Affairs Telephone: (direct): [contact] Email: [contact]

	No.: CP 64007	REV. D
	TITLE: Disrupt PAD+ Study	
	CLASS: CLINICAL PROTOCOL	PAGE 10 OF 57

3.0 INTRODUCTION

3.1 Background

Peripheral arterial disease (PAD) is one of the most common indications of atherosclerotic disease and impacts greater than 200 million people globally (Madhavan et al., 2020). PAD is caused by the accumulation of plaque in the arteries that do not supply the brain or the heart. The reduced blood flow may lead to pain, tissue loss and eventual foot/leg amputation or death. When the disease manifests in the peripheral arteries, it is usually indicative of a developing system-wide problem with atherosclerosis. If left untreated, PAD may significantly elevate the risk of cardiovascular disease morbidity and mortality (Davros, Garra, & Zeman, 1991).

Although it can involve the renal arteries and/or the arteries of the neck or arms, PAD normally develops in the lower extremities. Risk factors for PAD include hypertension, hypercholesterolemia, diabetes and smoking (Davros et al., 1991). Individuals with PAD are at risk for short-term cardiovascular ischemic events and can develop nonhealing wounds, gangrene, or may even need amputation in the affected limb (Bashir & Cooper, 2003; Davros et al., 1991). Diabetes and kidney disease can also cause clinical complications in individuals with PAD and can lead to a greater risk of limb amputations (Davros et al., 1991). The early diagnosis and treatment of PAD reduces an individual's risk of cardio- or cerebrovascular disease morbidity and mortality.

Percutaneous endovascular therapies are being increasingly employed as the primary revascularization treatment for disease of the superficial femoral artery and/or popliteal arteries, including calcified occlusions (Diamantopoulos & Katsanos, 2014; Jaff et al., 2015; Norgren et al., 2007; Roberts et al., 2014). Endovascular therapies include percutaneous angioplasty (PTA), nitinol stents, directional and rotational atherectomy, laser atherectomy, drug-eluting stents (DES) and drug-coated balloons (DCB) (Norgren et al., 2007).

Unmet needs in the management of PAD are driving the demand for new plaque modification tools, including Shockwave Medical's Peripheral Intravascular Lithotripsy (IVL). Intravascular Lithotripsy is a balloon-based technology that targets calcification to "normalize" vessel compliance prior to low pressure dilatation. Peripheral IVL is designed to optimize acute gain while minimizing acute vessel injury and reducing bail-out stenting. Pooled 30-day study results of the Disrupt PAD I and PAD II studies demonstrated compelling effectiveness and safety results of IVL in the treatment of moderately and severely calcified vessels with minimal vessel injury and only one stent implanted in 95 subjects. Acute effectiveness results showed high procedural success across all types of lesions and a large acute gain of 3.0mm after the procedure (Zeller, 2016). The PAD II 12-month results identified that optimal technique (with at least 1.1:1 IVL balloon to artery sizing and adequate therapeutic coverage) improves 12-month primary patency, resulting in a clinically-driven TLR rate of 8.6% without concomitant DCB or DES (Brodmann, Holden, & Zeller, 2018).

The Disrupt PAD III randomized trial is underway and will compare the optimal vessel preparation strategy prior to DCB in calcified femoropopliteal arteries. An interim analysis of the initial 200 patients treated in the PAD III Observational Study demonstrated consistent acute safety and

	No.: CP 64007	REV. D
	TITLE: Disrupt PAD+ Study	
	CLASS: CLINICAL PROTOCOL	PAGE 11 OF 57

effectiveness outcomes in a real-world population in a variety of calcified peripheral arteries and higher disease complexity (Adams et al., 2020). In addition, an interim analysis of IVL treatment in calcified iliac lesions in the PAD III Observational Study demonstrated IVL is safe and effective for the treatment of calcified iliac arteries and optimizes large-bore access (Armstrong et al., 2020).

3.2 Study Rationale

The Shockwave Medical M⁵ Peripheral IVL Catheter has FDA clearance and CE Mark approval and is indicated for lithotripsy-enhanced, low pressure balloon dilatation of calcified, stenotic peripheral arteries in patients who are candidates for percutaneous therapy. In an effort to continually optimize IVL therapy, the M⁵⁺ Peripheral IVL System represents an iterative catheter design change relative to the M5 device which (1) introduces a larger balloon size (8.0 mm), (2) extends the catheter working length from 110 cm to 135 cm, and (3) increases the frequency of IVL pulse delivery from 1 Hz (1 pulse per second) to 2 Hz (1 pulse per 0.5 seconds for all catheter sizes) with the goal of reducing overall procedure time. The objective of this study is to assess the safety and performance of the Shockwave M⁵⁺ Peripheral IVL System to treat calcified peripheral arteries in pre-market countries, and to assess continued safety and effectiveness in the US. It is being conducted as a post-market study in the US following FDA clearance of the M⁵⁺ catheter and as a pre-market study in Australia and New Zealand.

	No.: CP 64007	REV. D
	TITLE: Disrupt PAD+ Study	
	CLASS: CLINICAL PROTOCOL	PAGE 12 OF 57

4.0 STUDY DEVICE / TEST ARTICLE DESCRIPTION

4.1 Device/Test Article Description

The Shockwave Medical M⁵⁺ Peripheral IVL Catheter is a proprietary lithotripsy device delivered through the peripheral arterial system of the lower extremities to the site of an otherwise difficult to treat calcified stenosis. Energizing the lithotripsy device will generate pulsatile mechanical energy within the target treatment site, disrupting calcium within the lesion and allowing subsequent dilation of a peripheral artery stenosis using low balloon pressure. The IVL Catheter is comprised of an integrated balloon with an array of integrated lithotripsy emitters for the localized delivery of pulsatile mechanical energy. The system consists of the IVL Catheter, an IVL Connector Cable and an IVL Generator.

The M⁵⁺ IVL Catheter is available in nine (9) sizes: 3.5 x 60mm, 4.0 x 60mm, 4.5 x 60mm, 5.0 x 60mm, 5.5 x 60mm, 6.0 x 60mm, 6.5 x 60mm, 7.0 x 60mm, and 8.0 x 60mm. The M⁵⁺ Peripheral IVL Catheter is compatible with a 6 or 7 F sheath and has a working length of 135cm.

The Shockwave M⁵⁺ Peripheral IVL Catheter shaft contains an inflation lumen, a guidewire lumen, and the lithotripsy emitters. The inflation lumen is used for inflation and deflation of the balloon with 50/50 saline/contrast medium. The guidewire lumen enables the use of a 0.014" guidewire to facilitate advancement of the catheter to and through the target stenosis. The system is designed as 'Over-the-wire' (OTW) with 135cm shaft working length, so an exchange length (300cm) guidewire is indicated. The emitters are positioned within the balloon working length for delivery of pulsatile mechanical energy. The balloon is located near the distal tip of the catheter. Two radiopaque marker bands within the balloon denote the length of the balloon to aid in positioning of the balloon during treatment. The balloon is designed to provide an expandable segment of known length and diameter at a specific pressure. The proximal hub has one port each for inflation/deflation of the balloon, guidewire lumen, and connection to the IVL Connector Cable.

The IVL Catheter is supplied sterile via E-beam sterilization. It is intended for single use only and is not intended for reuse or re-sterilization. The Connector Cable and IVL Generator are non-sterile, reusable medical devices.

Refer to the Instructions for Use (IFU) provided for a complete product description.

4.2 Indication for Use

The Shockwave Medical M⁵⁺ Peripheral IVL System is indicated for lithotripsy-enhanced, low-pressure balloon dilatation of lesions, including calcified lesions, in the peripheral vasculature, including the iliac, femoral, ilio-femoral, popliteal, infra-popliteal, and renal arteries. This device is not intended for use in coronary, carotid, or cerebrovascular arteries.

	No.: CP 64007	REV. D
	TITLE: Disrupt PAD+ Study	
	CLASS: CLINICAL PROTOCOL	PAGE 13 OF 57

5.0 STUDY OBJECTIVES

The objective of this study is to assess the safety and performance of the Shockwave M⁵⁺ Peripheral IVL System to treat calcified peripheral arteries in pre-market countries, and to assess continued safety and effectiveness in the US.

5.1 Primary Endpoint(s)

Primary Safety Endpoint

Major Adverse Events (MAE) at 30 days defined as:

- Need for emergency surgical revascularization of target limb
- Unplanned target limb major amputation (above the ankle)
- Symptomatic thrombus or distal emboli that require surgical, mechanical or pharmacologic means to improve flow and extend hospitalization
- Perforations that require an intervention, including bail-out stenting

Primary Performance Endpoint(s)

Technical success is defined as final residual stenosis $\leq 30\%$ without flow-limiting dissection (\geq Grade D) of the lesion by angiographic core lab.

5.2 Secondary Endpoint(s)

Performance

- IVL Technical success is defined as residual stenosis $\leq 30\%$ without flow-limiting dissection (\geq Grade D) of the lesion post-IVL by angiographic core lab.
- Procedural success is defined as final residual stenosis $\leq 30\%$ without any flow-limiting dissection (\geq Grade D) in all target lesions by angiographic core lab.

Safety

- MAE at 6 and 12 months

Patency

- Primary patency at 12 months defined as freedom from clinically-driven target lesion revascularization (TLR) and freedom from restenosis determined by duplex ultrasound or angiogram $\geq 50\%$ stenosis. Acute PTA failure requiring a stent of the target lesion at any time during the index procedure will be counted as a loss of primary patency.
- Clinically driven target lesion revascularization (TLR) at 30 days, 6 and 12 months

Clinical

- Ankle-brachial index (ABI) at 12 months, reported as change from baseline
- Rutherford Category at 30 days, 6 and 12 months, reported as change from baseline

	No.: CP 64007	REV. D
	TITLE: Disrupt PAD+ Study	
	CLASS: CLINICAL PROTOCOL	PAGE 14 OF 57

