7.7.2 Index Procedure

Non-target lesions within a limb should be treated successfully prior to treatment of any target lesions. Non-target lesions may be treated with any commercially available device; treating a non-target lesion with a device that is unapproved or considered investigational will result in a protocol deviation.

A full description of the procedure is detailed in the Instructions for Use (IFU). The appropriately sized IVL balloon catheter should be selected per the IFU (select a balloon catheter size that is 1.1:1 based on balloon compliance chart and reference vessel diameter; the largest diameter

	No.: CP 64007	REV. D
	TITLE: Disrupt PAD+ Study	
	CLASS: CLINICAL PROTOCOL	PAGE 21 OF 57

balloon should be used if 1.1:1 sizing is not available). Once the IVL balloon is placed in the target lesion area, the balloon should be inflated to 4 atm and IVL treatment delivered for the pre-programmed time of 15 seconds to deliver 30 pulses. Note that the generator is programmed to force a minimum pause time of 10 seconds following every 30 pulses delivered. **Table 2** lists the pulsing sequence for IVL treatment.

Table 2: IVL System Sequence Chart

Treatment Frequency	2 Hz (1 Pulse every 0.5 Seconds)
Maximum Number of Continuous Pulses (1 cycle)	30 Pulses
Minimum Pause Time	10 Seconds
Maximum Total Pulses Per Catheter (10 cycles)	Displayed on generator

If the operator is unable to pass the IVL balloon through the lesion, a standard PTA balloon up to 3.0mm may be used for pre-dilatation prior to treatment with the IVL Balloon. All efforts should be made to pass the IVL balloon prior to use of a standard PTA balloon.

Following delivery of the first IVL cycle (30 pulses), inflate the balloon to the reference size using the Balloon Compliance Chart (refer to IFU) and record lesion response on fluoroscopy. Deflate the balloon and wait 10 seconds to re-establish blood flow. Repeat the steps above to complete a second delivery cycle of 30 pulses to complete a single treatment consisting of 60 pulses. Additional treatment cycles can be performed if deemed necessary.

If an additional lesion area needs to be treated, follow the treatment steps as identified per the IFU. The catheter can be advanced to the next treatment area. Confirm the balloon catheter is of the appropriate size for the next treatment area.

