Post-dilatation with a semi or non-compliant PTA balloon catheter should be completed when post-IVL results in one of the following below. The physician should use a 1:1 balloon catheter to artery ratio and may dilate for up to three minutes.

- Residual stenosis $\geq 30\%$ by visual estimate, or
- Presence of a flow-limiting (\geq Grade D) dissection, or
- Trans-lesional gradient >10 mm Hg is observed.

Follow the angiographic core lab guidelines to complete angiography showing all target lesions with reproducible landmarks for follow-up evaluation and assessment.

	No.: CP 64007	REV. D
	TITLE: Disrupt PAD+ Study	
	CLASS: CLINICAL PROTOCOL	PAGE 22 OF 57

Any commercially approved drug-coated balloon may be used after IVL. Provisional stenting should be performed with a bare metal or drug-eluting stent after primary treatment or post-dilatation balloon inflations are determined not to be successful. The angiographic core lab will confirm correct use of a stent based on the criteria above for subjects that receive a provisional stent. A provisional stent should be placed for an acute IVL failure defined as:

- Residual stenosis $\geq 50\%$ by visual estimate, or
- Un-resolved flow-limiting (\geq Grade D) dissection, or
- Trans-lesional gradient >10 mm Hg is observed.

Procedural Imaging Requirements

An angiographic cine image will be obtained for each lesion treated including pre-procedure, post-IVL and end of procedure. All angiographic images must be submitted to the core lab for analysis. Intravascular imaging (including IVUS or OCT) is optional. If performed, images from the three timepoints (pre-procedure, post-IVL and end of procedure) should be submitted to the Study Sponsor for analysis.

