9.2 Sample Size Determination

This study will enroll a minimum of 40 lesions in up to 40 subjects at up to 10 sites in Australia, New Zealand and the US with the aim of treating at least 20 target lesions with the 8.0 mm IVL catheter. A maximum of three target lesions may be treated per subject. The results from this study will provide estimates of the primary and secondary safety and performance endpoints. Two-sided 95% Confidence Intervals will be calculated for each endpoint.

As a confirmatory study, the sample size was justified using methods similar to those that would be used to justify a feasibility study. Sample sizes justifications in research and medical device development vary with four main methodological approaches: rules of thumb, conceptual models, numerical guidelines derived from empirical studies, and statistical formulas (J. Sim, Saunders, Waterfield, & Kingstone, 2018). For feasibility studies, the rule of thumb approach is most often applied, and sample sizes between 12 and 50 have been recommended (Browne, 1995; Hertzog, 2008; Julious, 2005; J. Sim & Lewis, 2012; Stallard, 2012). The sample size for the PAD+ study (n=40) is in keeping with these published recommendations and is therefore justified.

Assuming a primary performance point estimate of 65% for Procedural Success (derived from the PAD III study of peripheral IVL using the M⁵ catheter) (Gray, 2020), a sample size of 40 lesions would result in a 2-sided 95% CI of [48.3,79.4]. The lower bound of this interval is similar

	No.: CP 64007	REV. D
	TITLE: Disrupt PAD+ Study	
	CLASS: CLINICAL PROTOCOL	PAGE 27 OF 57

to the PTA (control) arm of PAD III study (50.4%) (Gray, 2020), which is sufficient given the aims of the research.

These data provide reasonable evidence of safety and performance.

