Fever: A temperature 38°C (>101.4° F) not related to a culture positive infection.

General Discomfort: Physical or psychosocial signs or symptoms commonly associated with hospitalization that are investigated and determined to require minor (i.e., aspirin, non-narcotic medication) or no treatment.

Hematoma: Collection of blood (or its degradation products) which exceeds 5 cm in diameter, requires treatment, or prolongs hospitalization.

	No.: CP 64007	REV. D
	TITLE: Disrupt PAD+ Study	
	CLASS: CLINICAL PROTOCOL	PAGE 47 OF 57

Hemorrhage: Any bleeding which results in a drop in hematocrit from pre-procedure level which is associated with hemodynamic compromise or which results in a hematocrit of $\leq 30\%$, or blood loss that requires transfusion.

Hypertension: Systolic BP >140 mmHg, or diastolic >90 mmHg requiring specific medical therapy.

Iliofemoral DVT: Defined as DVT involvement of the common or external iliac veins or the common femoral vein, with or without distal (e.g., toward foot) DVT involvement, based on duplex ultrasound exam.

Infection, access site: Infection at the vascular access site, documented by lab culture or clinical evidence requiring medical treatment (irrigation, debridement, antibiotics, etc.) to resolve.

Infection, sepsis: Culture-proven infections or presumptive treatment with antibiotics for clinically diagnosed infection.

Infection, systemic: Systemic infection documented by positive lab culture or clinical evidence, requiring medical treatment to treat and resolve.

Intracranial Hemorrhage: Includes all bleeding within the cranium either subarachnoid, intraparenchymal, or intracerebral.

Intravascular Lithotripsy (IVL), formerly known as Intravascular Lithoplasty: Shockwave Medical's proprietary balloon angioplasty catheter including lithotripsy technology that creates pulsatile mechanical energy for disrupting calcified vascular plaque.

Limb Ischemia: Deficient supply of oxygenated blood to the tissues in the limbs that is due to obstruction of the inflow of arterial blood characterized by pain and/or discoloration of the limb.

Lithotripsy: A medical procedure for disrupting calculus in the body.

Luminal Patency: Post-procedure residual stenosis $<50\%$ as determined by investigator visual assessment or quantitative analysis of the end of procedure angiogram.

Major Adverse Event (MAE): For the purposes of this study, the definition of Major Adverse Event(s) includes:

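### Does the stent rule for primary patency miss stents placed for IVL failure because Section 5.2 says PTA failure?

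*Combined protocol and SAP*

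**What the plan says.** Section 5.2 defines primary patency at 12 months by two conditions: no clinically driven target lesion revascularization, and no restenosis of 50% or more on duplex or angiogram. It then adds a rule on when patency is lost: "Acute PTA failure requiring a stent of the target lesion at any time during the index procedure will be counted as a loss". The term acute PTA failure occurs nowhere else and has no entry in Section 15.1. The synopsis in Section 2.0 gives the patency definition without the stent sentence.

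Section 7.7.2 uses a different term: "A provisional stent should be placed for an acute IVL failure defined as", followed by three criteria. It places provisional stenting "after primary treatment or post-dilatation balloon inflations are determined not to be successful", and says that "The angiographic core lab will confirm correct use of a stent based on the criteria above".

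The word PTA is used in several ways:
- In 7.7.2, if the IVL balloon will not cross, "a standard PTA balloon up to 3.0mm may be used for pre-dilatation". After IVL, "Post-dilatation with a semi or non-compliant PTA balloon catheter should be completed" when any of three findings is present. Both are balloons other than the study device.
- In Section 9.2 it names a comparator, the "PTA (control) arm of PAD III study".
- In Section 3.1 it stands for percutaneous angioplasty in general, and Section 15.1 describes IVL as a "proprietary balloon angioplasty catheter including lithotripsy technology".

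**The concern.** The endpoint rule rests on an undefined term, while the procedure section defines a near neighbour. If PTA in 5.2 means only the pre- and post-dilatation balloons, a stent placed straight after IVL, with no PTA balloon used, would not be an acute PTA failure and would not count against patency. That would be odd in a study of IVL: the failure most relevant to the device would be the one left out. Section 7.7.2 seems to leave that route open, since it allows a stent after primary treatment or after post-dilatation.

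A second gap concerns perforation. The MAE definition in Section 5.1 foresees bail-out stenting for it, but perforation is not among the acute IVL failure criteria.

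With about 40 lesions, a few stents classified one way or the other would be visible in the reported patency, and in an unblinded single-arm study it is better not to make that choice after seeing the data.

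**Working it through.** No stated figure in the plan depends on this rule, so the main check is textual: compare the two lists in 7.7.2.

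| Finding | Trigger for PTA post-dilatation | Trigger for provisional stent | Does the stent trigger imply the other? |
|---|---|---|---|
| Residual stenosis, visual estimate | 30% or more | 50% or more | Yes |
| Dissection of Grade D or worse | Present | Unresolved | Yes |
| Trans-lesional gradient | Above 10 mm Hg | Above 10 mm Hg | Yes, identical |

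**Step 1.** A lesion that meets a stent trigger after IVL also meets a post-dilatation trigger. Section 7.7.2 says post-dilatation with a PTA balloon should then be completed. A lesion handled as the section describes has had PTA before a provisional stent, so its stent follows a failed PTA even in the narrow sense. The narrow and broad readings of 5.2 agree for these lesions.

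**Step 2.** What is left is a stent placed without prior post-dilatation, a stent placed for perforation, and a stent that meets none of the criteria. The first requires a departure from the post-dilatation step. For all three, the timing words in 5.2 take in the whole index procedure, and Sections 3.1 and 15.1 support reading angioplasty broadly enough to include IVL.

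**Step 3.** The core-lab sentence does not alter this. It points to criteria above it, yet the acute IVL failure list stands below it; the list above is the one for post-dilatation. The pointer is unclear, but it concerns whether a stent was used correctly, and 5.2 does not make loss of patency depend on that check.

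**Step 4: size.** The inputs are 40 lesions (Sections 6.2 and 9.2), one stent in 95 subjects in the pooled PAD I and II results (Section 3.1), and exact intervals for proportions (Section 9.1). Three assumptions are mine: patency is analysed per lesion, the per-subject stent rate applies per lesion, and 32 of 40 lesions are patent before the rule is applied.
- Shift per reclassified lesion: 100/40 = 2.5 points. If only 36 lesions had known status (10% missing, assumed), 100/36 = 2.8 points.
- Example: 32/40 = 80.0%, exact 95% CI 64.4 to 90.9. With one lesion moved, 31/40 = 77.5%, 61.5 to 89.2. The first interval is 90.9 − 64.4 = 26.5 points wide, so one lesion moves the estimate by about a tenth of that width.
- Expected stents of any kind: 40 × 1/95 = 0.42. Chance of none: (94/95)^40 = 65.5%.
- The exact 95% CI for 1/95 is 0.03% to 5.73%. At the upper limit, 40 × 0.0573 = 2.3 stents are expected.

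These counts cover all stents. The unclear cases in Step 2 are a subset, and the documents give no rate for them or for perforation stents.

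**The case for a change.** The strongest case for a change is that the words fixing when a stent counts do not fix why it was placed. Section 7.7.2 does mention a stent after primary treatment, so a stent straight after IVL is not excluded by the text. Even the broad reading does not plainly settle a perforation stent, because a perforation is a complication rather than a failure to open the lesion. Stent use in this population, which includes iliac arteries and a larger balloon, could exceed 1 in 95. The remedy would cost only a sentence or two.

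Much of that is accurate as description: the term is undefined, the core-lab pointer is unclear, the synopsis omits the rule, and the patency status of perforation stents is unstated. What does not stand is the inference that failures of the study device escape the endpoint. The trigger lists rule that out for lesions handled as 7.7.2 describes.

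The remaining cases are few and would not be hidden. A perforation that needs a stent is a major adverse event within the primary safety endpoint, whatever its patency status; whether it should also count against patency is a design preference. Criteria for clinical endpoints are assigned to the Clinical Events Committee charter (Section 13.1), and the case report forms are a separate attachment. Neither is available here, so it cannot be said that the detail is missing. The synopsis is a shorter summary, not a conflicting rule.

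**Conclusion.** The mismatch between PTA failure in 5.2 and IVL failure in 7.7.2 is real, but it is a matter of wording. A provisional stent placed as 7.7.2 describes counts as loss of patency on either reading. For the few other index-procedure stents, the natural reading of 5.2 is to count them, and an analyst can do so and list each one.

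If patency is analysed per lesion, each doubtful lesion that would otherwise be patent moves it by at most 2.5 points at 40 lesions, or 2.8 at 36. Section 5.2 does not name the unit, and 9.1 speaks of subject counts; per subject the shift would be 100/N for N subjects, which is larger than 2.5 points if fewer than 40 are enrolled. The endpoint is secondary and descriptive, with no hypothesis or threshold attached, so no conclusion of the study turns on the difference. The judgement rests on 7.7.2 being followed for post-dilatation and on stent use being of the order seen in the earlier studies; it takes no view on when a stent should be placed. No change to the plan is called for.
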